Upon enrollment and completion of the informed consent process, patients will be randomized into the 2 study groups of 60 each, based on a list compiled by a random number generator prior to initiation of the study. Both Groups will complete the Western Ontario and McMaster Universities Osteoarthritis Index (WOMAC), and the Subjective International Knee Documentation Committee Subjective Score (IKDC) questionnaires prior to any treatment. Due to the invasive nature of obtaining marrow aspirate blinding of the subjects and clinicians will not be performed. Group 1 [PRP]: Will receive a single (1) intra-articular injection of PRP. Group 2 [BMC]: Will receive a single (1) intra-articular injection of BMC after obtaining informed consent. Both types of injections and all associated procedures will be performed in the clinic or lab setting with local anesthesia. Following the injection patients will be asked to complete a short questionnaire documenting the BMC or PRP collection, preparation and injection experience. Ten patients will be randomly selected from both (20 total subjects) the PRP and

BMC groups to have analysis performed on the BMC and PRP as described below. This analysis will not be performed on patients not randomly selected. In patients randomly selected after the BMC or PRP have been prepared for injection, a small sample (1 mL) of the BMC or PRP will be separated and sent to an independent lab (Biosciences Research Associates, Inc) for analysis. The PRP will be analyzed with a CBC and the BMC will be analyzed for TNC, human CD34+ hematopoietic stem/progenitor cell assay, CFU-F, plasma free hemoglobin, cell viability percent, and hemolysis percent. Evaluation, a 4 view x-ray series (long leg, lateral, sunrise, and bilateral Rosenberg), and injections will be provided at no charge to the patients. Patients will then be given standard follow-up care instructions that include no use of NSAIDS for at least 7 days and partial weight bearing on the limb for 2-3 days, followed by the initiation of a standard physical therapy program at one week following injection.

After the injection subjects will be required to complete the WOMAC and IKDC questionnaires as well as report any medications they are using via email or phone (paper method will be available on request) at 1, 3, 6, 9, 12, 18, and 24 months following the injection.

PRP protocols

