All personal information is strictly confidential and no names will be disclosed except as required by law. All research information will be managed and accessible by only the named investigators and their medical staff. Data sheets will have names and identifying information replaced with a subject code to protect the confidentiality of the subject. All information provided by the subject during this project will be recorded on the appropriate forms and stored in a locked room in the AREF research facility. In addition all subject data forms will be scanned and stored, along with summary information forms, spreadsheets, and photos, in a secure password protected folder on a laptop in which only study investigators will have access to, and will be permanently deleted following any and all publications or presentations have been completed related to this research. All records related to this research will be retained in a secure location for a period of 3 years following the completion of all study related activities, at which time they will be properly destroyed.

8 Data Analysis

All data will be entered into an excel spreadsheet for analysis that will include obtaining standard measures such as means and standard deviation. Data will be analyzed as scores on the two questionnaires as well as across subsets of the individual questionnaires for function, quality of life and pain scores. Additional determinations based on medication usage and failure rates will be examined as well.

9 Statistical Considerations

A power analysis was performed to determine sample size based upon recent clinical trials comparing PRP to HA for the treatment of osteoarthritis. Analysis utilized the average of standard deviation to detect average of group mean effect at 80% power. This determined that 25 patients per group would be needed to reach statistical significance with the WOMAC and that 50 patients would be needed per group for the IKDC. Considering a potential dropout rate of 20%, 60 patients per group was chosen as the sample size.

Data will be analyzed for differences between groups using a repeated measures ANOVA design, using a significant p-value of < 0.05 for rejecting the null hypothesis. Additional subjective analysis will be performed on data involving the patient experience with regards to the injection.

10 Quality Control and Assurance

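### The plan does not say which score, which ANOVA contrast or which use of the pre-treatment score decides the trial, so the 5% error rate holds per test and not for the trial's claim

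*Combined protocol and SAP*

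**What the plan says.** Section 9 (Statistical Considerations) holds the only test: "Data will be analyzed for differences between groups using a repeated measures ANOVA design, using a significant p-value of < 0.05". No adjustment, testing order or sidedness is given.

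Section 8 (Data Analysis) says the data will be analysed "as scores on the two questionnaires as well as across subsets of the individual questionnaires for function, quality of life and pain scores".

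Section 9 sizes the trial twice: "25 patients per group would be needed to reach statistical significance with the WOMAC" and "50 patients would be needed per group for the IKDC". Neither total is called primary. The sizing inputs are "based upon recent clinical trials comparing PRP to HA for the treatment of osteoarthritis"; no effect size or SD is printed.

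Section 5 (Study Design and Procedures) collects both scores before injection ("questionnaires prior to any treatment") and again "at 1, 3, 6, 9, 12, 18, and 24 months following the injection". That makes eight assessments, one before treatment and seven after. The document does not say what role the pre-treatment score has in the ANOVA. The Section 2 objective is pain and function at several time points, with no deciding visit.

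**The concern.** One threshold is applied to at least two total scores. A two-group repeated measures ANOVA also yields both a group term and a group-by-time term, and the pre-treatment score can be handled in several ways. If IKDC is significant and WOMAC is not, or the two terms disagree, the plan cannot say whether BMC and PRP have been shown to differ. The deciding rule could then be settled after the results are known, and the nominal 5% would describe each test but not the trial's conclusion.

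The baseline gap has a second consequence, which concerns power. If the pre-treatment visit is a level of the time factor, the group term averages in a visit at which no treatment effect can exist.

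**Working it through.** **1. The plan's own figures.** The 25 and 50 per group cannot be recomputed, because no effect size or SD is given. The 60 per group matches 50 × 1.2 = 60. With 20% dropout, 60 × 0.8 = 48 per arm remain, and 48 is used below.

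**2. Error rate across the two totals, group test only.** Assumptions: no true difference, two-sided 0.05, test statistics bivariate normal with correlation ρ. The documents do not give ρ, so a range is shown.

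- P(either) = 1 − P(|Z₁| < 1.96 and |Z₂| < 1.96)
- P(both) = 0.05 + 0.05 − P(either)

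| ρ | Either total significant | Both significant |
|---|---|---|
| 0.5 | 9.1% | 0.9% |
| 0.7 | 8.3% | 1.7% |
| 0.9 | 7.0% | 3.0% |

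Holm over the two totals brings the chance of any false rejection to 4.7% (ρ = 0.5) down to 3.6% (ρ = 0.9).

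**3. Illustrative extensions.** These need assumptions beyond the text.

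- One score, group or group-by-time term: 9.7% with eight time levels and 10.1% with seven (20,000 simulated trials, 48 per arm, compound symmetry, within-patient correlation 0.5, complete data).
- One score, group effect, best of four baseline treatments (level, ignored, change score, covariate): about 12% (simulated at 50 per arm, compound symmetry). This applies only if the choice is made after seeing results.
- Any of five scores, group test: 18% (ρ = 0.5) to 10% (ρ = 0.9). Five is an assumed count.

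**4. Effects implied by the stated sizes.** Solving a two-sided 0.05 t-test for 80% power gives d = 0.809 (WOMAC, 25 per group) and d = 0.566 (IKDC, 50 per group). They derive from PRP-versus-HA trials, so they are only a guide for BMC versus PRP.

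**5. Power for IKDC at 48 per arm.** Let w be the within-patient correlation (assumed 0.5 to 0.9), with a constant effect after injection and complete data.

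- Mean of the seven post-injection visits: effect d, SD factor √((1 + 6w)/7).
- Group term with the pre-treatment visit as an eighth level: effect d × 7/8, SD factor √((1 + 7w)/8).

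| w | Seven-visit mean: standardised effect | Power | Eight-level group term: standardised effect | Power |
|---|---|---|---|---|
| 0.5 | 0.566/0.756 = 0.749 | 95% | 0.495/0.750 = 0.660 | 89% |
| 0.9 | 0.566/0.956 = 0.592 | 82% | 0.495/0.955 = 0.518 | 71% |

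With eight levels, the group-by-time term for IKDC has 76% power at w = 0.5 and over 99% at w = 0.9 (noncentral F on 7 and 658 df). Which term decides therefore matters for power as well as error. None of these figures includes covariate adjustment for baseline, which would raise the seven-visit figures.

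**The case against.** The best defence is that the plan is less open than it looks. The sample size covers the larger requirement (50, not 25), which fits an intention to power both totals. If both had to be significant, the error rate would be below 5%. This reading is plausible, but it is not written down. The larger requirement is equally compatible with either total being enough, and it does not make IKDC primary.

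A second defence is that testing for differences between groups means the group term. That is the more natural reading, though the text does not exclude the interaction. On the group term alone the either-total rate is still 7% to 9%. The phrase "detect average of group mean effect at 80% power" does not settle the matter, because it describes inputs to the sample size calculation and not the ANOVA term.

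Third, the either-term figure depends on the model. If correlation decays over the visits (assumed 0.90 to 0.95 per month) and no sphericity correction is made, it is about 13% to 14% for one score instead of about 10%. The five-score figures treat every subscale as able to decide the trial, which Section 8 does not say. That criticism stands, so neither set is used for the conclusion.

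Fourth, treating baseline as a level of the time factor is not wrong in itself. A longitudinal model of that kind with a pre-named contrast on change is valid. The fault is the absence of any stated contrast.

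**Conclusion.** The point holds. One unadjusted 0.05 rule covers two separately sized totals, and the either/both rule, the deciding contrast and the role of the pre-treatment score are all missing. For the two named totals on the group test, the false-positive rate is about 7% to 9% if either may support a claim and 0.9% to 3.0% if both must, for assumed between-score correlation 0.9 to 0.5. The supported conclusion is that the rate is not controlled at 5% and can exceed it.

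Separately, using the pre-treatment visit as a time level lowers IKDC power from 82%–95% (seven-visit mean) to 71%–89% (group term), under the assumptions shown.

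A reader might infer more. The documents do not show that the error rate is in fact inflated, because that depends on a success rule they do not give. They do not support 10% to 18% as the trial's rate, since the number of subscale tests is unknown and nothing says each can decide the trial. The lack of blinding of subjects and clinicians is not what permits a test to be chosen after the fact; a blinded trial with this wording would have the same gap.

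**What to change.** Before outcome data are analysed, add to Section 9:

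1. **Score rule.** Name one primary total and test the other at 0.05 only if the first is significant. Alternatively, require both totals to be significant, or use Holm over the two if either may support the claim. If a pain or function score is preferred, to match the Section 2 objective, name it as primary.
2. **Contrast.** Name one between-group contrast from the repeated measures model, either over the seven post-injection visits or at one pre-named visit, at two-sided 0.05. Adjust for the pre-treatment score, either as a covariate or in a longitudinal model that keeps it as a level with a pre-named change-from-baseline contrast.
3. **Everything else.** Report other terms, subscales and visits as exploratory estimates with 95% confidence intervals.

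The sponsor chooses among these options. No extra patients or data are needed.

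The cost falls on the second claim. At 48 per arm, with the effects implied above and a single-visit t-test, power is about 97% for WOMAC and 78% for IKDC. WOMAC first loses almost nothing. IKDC first limits a WOMAC claim to about 78%, and requiring both also gives about 78%. Holm gives 95% to 96% for WOMAC and 78% for IKDC. On the seven-visit mean, IKDC first limits a WOMAC claim only to about 81% to 95%. Subscales carry no confirmatory claim unless one is made primary.

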While PRP shows promise in helping restore function to these patients, there are still concerns with PRP's long term outcomes. Another option that has become more popular for physicians treating this debilitation condition is bone marrow aspirate concentrate (BMA), which uses undifferentiated cells found in the bone marrow to promote healing and tissue

regeneration.¹³ These cells have the ability to replicate into a multiple different tissue types. With BMA, the marrow is concentrated provide better healing of the damaged tissue and aid in growth and repair. The full benefits of BMA are still unknown, but studies have shown the treatment can reduce swelling, relieve pain, and improve healing in articular cartilage and bone grafts.¹⁴

Autologous BMA has shown promising clinical potential as a therapeutic agent in regenerative medicine, including the treatment of osteoarthritis and cartilage defects,¹³⁻¹⁴ and the clinical efficacy platelet rich plasma has been documented to alleviate symptoms related to knee osteoarthritis.²⁻⁸ However, randomized, prospective comparison of the two techniques has not been reported in the literature and long term follow-up for both treatments is limited, and especially limited in the use of BMA for osteoarthritis treatment.

2 Objectives

The main objective of this study is to compare the effectiveness of bone marrow aspirate concentrate (BMC) to platelet rich plasma (PRP) injections for the treatment of knee osteoarthritis in regards to pain and function at multiple time points up to 24 months post injection.

3 Subject Eligibility

Patients between the ages of 18 and 80, with evidence of knee osteoarthritis will be screened for eligibility in the study. All subjects must present with pain or swelling of the knee of at least 4 months in duration and a Kellgren-Lawrence score between 1

and 3 upon x-ray evaluation. Potential subjects must be willing and able to provide informed consent and be willing and able to return for scheduled follow-up visits.

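### Section 9 names only a repeated measures ANOVA for eight records per patient, with no baseline adjustment, missing-data method or analysis population; the main loss is precision, with a secondary risk of bias from unequal dropout

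*Combined protocol and SAP*

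**What the plan says.** All references are to the combined protocol and SAP.

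- **Section 5 (Study Design and Procedures).** Both groups complete the WOMAC and IKDC "questionnaires prior to any treatment", and again "via email or phone (paper method will be available on request) at 1, 3, 6, 9, 12, 18, and 24 months following the injection". That is eight planned records per questionnaire. The same section says that "blinding of the subjects and clinicians will not be performed".
- **Section 2 (Objectives).** The comparison of the two treatments is "in regards to pain and function at multiple time points up to 24 months post injection".
- **Section 9 (Statistical Considerations).** The only method named for the group comparison is in the sentence "Data will be analyzed for differences between groups using a repeated measures ANOVA design", tested "using a significant p-value of < 0.05 for rejecting the null hypothesis". The sample size paragraph begins its last step with "Considering a potential dropout rate of 20" percent and arrives at 60 per group.
- **Section 8 (Data Analysis).** Scores go into a spreadsheet, and "Additional determinations based on medication usage and failure rates will be examined as well". Failure is not defined, and no link is made between failure and a missing score.

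No section says which form the ANOVA takes, which of its effects is the treatment test, whether baseline is a covariate or a level of time, who is analysed, or what happens to incomplete records.

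**The concern.** The plan expects one patient in five to be lost, yet its only named method, in its classical form, needs a complete set of records. Two things follow if that form is used.

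First, information already paid for is left out. A patient missing one form leaves the analysis of that questionnaire, and the group main effect takes no account of where the patient started. The baseline score is the more valuable of these two omissions.

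Second, the patients compared may no longer be the groups that were randomised. If dropout works the same way in both arms, a completers' comparison keeps its 5% error rate under the null. If poor results lead to dropout more in one arm than in the other, it need not. That is possible here because patients know which procedure they had and report their own outcomes for two years.

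As written, who is analysed and how can be settled after the data have been seen, in a trial where treatment is known to patients and clinicians.

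**Working it through.** **1. The plan's own figures.** 50 × 1.20 = 60 per group, as stated. (50 / 0.80 = 62.5 would give 63; that is a separate point.) Complete cases at 20% dropout: 60 × 0.80 = 48 per group, so 24 of 120 patients are excluded.

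**2. Forms left unused.** Suppose the 12 dropouts per arm are spread evenly over follow-up. Each then returns 0 to 6 follow-up forms (mean 3) plus baseline, or 4 forms. Unused share = 12 × 4 / (48 × 8 + 12 × 4) = 48 / 432 = 11%. Simulation gave 10.5%, or about 21% if a further 2% of forms are missed (an assumed rate).

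**3. Precision.** The documents give no correlations, so I assume 0.4 + 0.4·exp(−months/12) between visits, in SD units. The variance of the mean of 7 follow-ups is 0.653, and 0.292 after baseline adjustment. With SE = √(2 × variance / 48):

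| Analysis | SE | SE with lower correlations, 0.2 + 0.4·exp(−months/12) |
|---|---|---|
| Completers, unadjusted | √(2 × 0.653/48) = 0.165 | 0.142 |
| Completers, baseline-adjusted | √(2 × 0.292/48) = 0.110 | 0.116 |
| Mixed model, all forms (simulated) | 0.104 | 0.111 |

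Most of the gain comes from baseline adjustment; partial records add a smaller step.

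**4. Power at 48 per arm.** No effect size or SD is given. Solving a two-sample t test at n = 50, 80% power and two-sided 0.05 (sidedness assumed) gives d = 0.566 for the IKDC. A single visit has 78% power. For the averaged test, d is divided by the SD of the mean; if baseline is an eighth level, a constant follow-up effect is also diluted by 7/8.

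| Assumed correlation | 7-follow-up mean | Eight levels |
|---|---|---|
| 0.2 + 0.4·exp(−months/12) | 98% | 94% |
| 0.4 + 0.4·exp(−months/12) | 92% | 85% |
| 0.6 + 0.3·exp(−months/12) | 87% | 78% |

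With 2% of follow-up forms also missed, 48 × 0.98⁷ = 41.7 per arm are complete, and the middle eight-level figure falls from 85% to 79%.

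**5. Bias (simulation).** Settings: 60 per arm, no true effect, 20% dropout in each arm, the middle correlations, and 3,000 to 6,000 trials per case. The dropout hazard depends on the last score, with an assumed log-odds of 1.3 per SD unless stated. For completers:

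| Test | Dropout link | Absolute bias (SD) | Type I error |
|---|---|---|---|
| Main effect, unadjusted | Same in both arms | 0.00 | 5% |
| Main effect, unadjusted | Half as strong in one arm | 0.07 | 7% |
| Main effect, unadjusted | 0.65, one arm only | 0.09 | 9% |
| Main effect, unadjusted | 1.3, one arm only | 0.16 | 16–17% |
| Baseline-adjusted | 1.3, one arm only | 0.06 | 9% |
| Change from baseline | 1.3, one arm only | below 0.01 | 4–5% |
| Group-by-time F, Greenhouse-Geisser | 1.3, one arm only | – | 4.9% |

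With the lower correlations, the one-arm-only case gives 0.12 SD and 14% unadjusted, and 0.07 SD and 10% baseline-adjusted.

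**6. The mixed model under the same dropout links.** Bias is at most 0.002 SD and type I error is 4.6% to 5.1%. This used maximum likelihood means and a t test without the Kenward-Roger correction, so it approximates the model proposed below. If dropout in one arm depends on the unseen score, the model is biased too: 0.04 SD and 6%, against 0.16 SD and 17% for unadjusted completers.

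**The case against.** The strongest reply is that Section 9 speaks only of differences between groups and does not choose the main effect. With baseline as a level of time, group-by-time is the usual treatment test. On the same completers in the extreme case, that F test rejects 4.9% of the time with the Greenhouse-Geisser correction and 6.7% without, against 4.6% and 6.3% with no selective dropout. Selection shifts baseline along with follow-up, so it largely cancels in change scores. This stands. The bias figures belong to particular tests, and the sphericity issue is minor.

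A second reply is that comparing a baseline-adjusted mixed model with an unadjusted ANOVA mixes two changes. This also stands, and is why the steps are shown separately: adjustment alone takes the SE from 0.165 to 0.110 SD and the extreme-case bias from 0.16 to 0.06 SD.

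A third is that no document supports the dropout links or correlations. That is true; they are illustrations, and with a half-strength difference between arms the error rate is 7%.

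A fourth is that making the follow-up average decisive would set the estimand, whereas Section 2 speaks of several time points. The fix therefore reports every visit and leaves the choice of primary contrast to the sponsor.

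None of these replies supplies the missing specification.

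**Conclusion.** The point holds as a specification gap with a measurable cost, and the plan should be amended before analysis. Under the middle assumed correlations, the unadjusted completers' ANOVA has an SE for the averaged difference about 1.6 times that of the proposed model (0.165 / 0.104); with the lower correlations the ratio is about 1.3 (0.142 / 0.111). Bias is secondary and needs outcome-related dropout that differs by arm.

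Three stronger readings are tempting, and the documents support none of them.

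- *A reader might infer that the sponsor will delete incomplete patients.* The plan does not say so; it leaves the form of the ANOVA open, and exclusion is a property of the classical form, applied to each questionnaire separately.
- *A reader might infer that the planned ANOVA carries a 17% false-positive rate.* That figure is for the unadjusted main effect among completers, with a strong dropout link in one arm only. It must not be applied to group-by-time, change-from-baseline or baseline-adjusted forms.
- *A reader might infer that power is inadequate, or that it is assured.* At 48 per arm the averaged test has about 78% to 98% power in the cases examined, depending on the correlations and on whether baseline is a level, and less if further forms are missed.

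All these figures assume a constant effect and dropout spread over follow-up. The document facts are certain; the sizes are only as good as the assumed correlations and dropout links.

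**What to change.** Replace the ANOVA sentence in Section 9 with:

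> For each questionnaire score, the 7 follow-up scores will be analysed with a mixed model for repeated measures (REML, unstructured covariance, Kenward-Roger degrees of freedom) with group, time, group-by-time, baseline score and baseline-by-time. Patients are analysed in the group assigned, and all randomised patients with at least one follow-up form contribute every available form. If the model does not converge, a spatial-power (continuous-time) covariance with visit-specific variances, which allows for the uneven visit spacing, is used. The group difference averaged over the 7 follow-ups is tested at two-sided p < 0.05, and the group difference at each visit is reported with its 95% CI.

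State that this average excludes baseline, unlike the group effect of an eight-level ANOVA. Which contrast and which questionnaire is primary is for the sponsor to choose in advance.

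Because the model assumes data missing at random, add one sensitivity analysis: multiple imputation within group, with imputed scores after dropout shifted toward worse by 0 to 1 baseline SD, in each arm separately and in both. This also brings in patients with no follow-up form (about 2 of 60 per arm in the simulation), whom the main model cannot use. About 12% of planned follow-up forms are missing in the simulation at 20% dropout, so a 1 SD shift in one arm moves the averaged difference by about 0.12 × 1 = 0.12 SD.

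Cost: new wording, export from the spreadsheet to mixed-model software, and slightly more analysis work. No extra patients or data are needed.

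### The repeated measures ANOVA in section 9 has no sphericity correction or covariance model, so visit-by-visit comparisons of the arms could run above 5% if correlation falls with time between visits

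*Combined protocol and SAP*

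**What the plan says.** Section 9 (Statistical Considerations) holds the whole inferential plan: "Data will be analyzed for differences between groups using a repeated measures ANOVA design". The significance level is 0.05. The section does not say which effect is tested (group or group by time), what covariance is assumed, whether sphericity is checked or corrected for, or what error term a comparison at a single visit would use. It does not rule out a correction either.

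Section 5 (Study Design and Procedures) sets the occasions. Both groups complete the WOMAC and IKDC "questionnaires prior to any treatment" and again "at 1, 3, 6, 9, 12, 18, and 24 months following the injection". That makes eight occasions if baseline enters the model and seven if it does not.

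Section 2 (Objectives) asks how the arms compare on pain and function at several follow-up times out to 24 months. Section 8 (Data Analysis) mentions means and standard deviations; it describes no confidence intervals or model-based error bars.

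**The concern.** A classical repeated measures ANOVA tests the group-by-time effect against one pooled within-patient error term. That term is right only under sphericity, meaning that the difference between any two visits has the same variance. Questionnaire scores one month apart usually agree more closely than scores 24 months apart, and sphericity then fails. This happens even with complete data, so it is separate from dropout.

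The group main effect does not rely on sphericity. However, it compares the arms on a score averaged over all visits, possibly including baseline, when no treatment effect can exist. It cannot say whether the arms differ at 12 or 24 months. The objective needs group-by-time tests or comparisons at single visits, and those are the analyses exposed to the problem. Because the plan is silent, the choice between corrected and uncorrected tests, and between pooled and visit-specific errors, could be made after the data are seen.

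**Working it through.** The plan states no figure on this point (no epsilon, correlation or group-by-time error rate), so there is nothing of its own to reproduce. The check asks how far an uncorrected analysis could drift from 5%.

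**Inputs from the documents**
- Occasions: months 0, 1, 3, 6, 9, 12, 18 and 24 (section 5), so k = 8.
- Patients: "patients will be randomized into the 2 study groups of 60 each" (section 5). Section 9 expects 20% dropout, so 60 × 0.8 = 48 complete per group.
- Level: 0.05 (section 9). The F test is non-directional; contrasts are taken as two-sided.

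**Assumed, because the documents are silent**
- Variance is 1 at every visit, and the correlation r depends on the gap D in months. Several forms are used to give a range. Noise means an independent measurement-error share at each visit.

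**Formulas**
- Let S be the covariance matrix, C = I − J/k (J all ones) and A = CSC. Then epsilon = tr(A)² / [(k − 1) tr(A²)]. Epsilon is 1 under sphericity.
- Expected pooled within-patient error: MSE = tr(A)/(k − 1). With unit variances this is 1 minus the mean correlation between visits.
- Change from baseline to visit j has true variance V = 2(1 − r). The pooled term treats it as 2 × MSE. SE ratio (true/pooled) = √(V / (2 × MSE)).
- Large-sample rejection rate of the pooled-error contrast under the null = 2[1 − Φ(1.96 / ratio)].

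**One case in full:** r = 0.4 + 0.4 exp(−D/6), with noise share 0.2.
- At 24 months r = 0.4 + 0.4 × 0.0183 = 0.407, so V = 2 × 0.593, about 1.185.
- MSE = 0.4835, so 2 × MSE = 0.967.
- Ratio = √(1.185/0.967) = 1.107, and 1.96/1.107 = 1.77, giving a rejection rate of 7.7%.
- At 1 month r = 0.739, V = 0.523 and the ratio is 0.735. The same contrast rejects under 1%.

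**All cases** (48 per arm, no treatment effect; the group-by-time column comes from 8,000 simulated trials per row):

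| Assumed r for gap D | Noise | r at 1 / 24 mo | Epsilon | Group-by-time, uncorrected | 24-mo change, pooled error: SE ratio, rejection |
|---|---|---|---|---|---|
| 0.4 + 0.4 exp(−D/6) | 0.2 | 0.74 / 0.41 | 0.82 | 6.2% | 1.11, 7.7% |
| 0.2 + 0.6 exp(−D/12) | 0.2 | 0.75 / 0.28 | 0.72 | 6.9% | 1.19, 10.0% |
| 0.3 + 0.6 exp(−D/6) | 0.1 | 0.81 / 0.31 | 0.71 | 7.2% | 1.15, 8.7% |
| 0.3 + 0.7 exp(−D/6) | none | 0.89 / 0.31 | 0.62 | 8.3% | 1.18, 9.6% |
| exp(−D/12) | none | 0.92 / 0.14 | 0.48 | 9.3% | 1.30, 13.2% |
| equal correlations | – | equal | 1.00 | 5.3% | 1.00, 5.0% |

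With the Greenhouse-Geisser correction, the group-by-time test in the decaying rows rejects 4.5-5%. The pooled-error change contrast rejects 6.5-7.8% at 12 months and under 1% at 1 month. Repeat simulations of the decaying rows gave 6.2-10.1% and 6.3-9.5% for the uncorrected test, and 7-14% for the 24-month contrast, against about 5% with a visit-specific error.

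**A second set of structures** (20,000 trials each, 120 and 96 patients in total):
- 80% exponential decay plus 20% noise: 7.1-7.7% uncorrected.
- Pure exponential decay with a 12-month correlation of 0.3, 0.5 or 0.7: 8.7-10.6% uncorrected.
- Over all structures tried, the Greenhouse-Geisser test runs at 4.3-5.2%, and the group main effect at 4.6-5.3% with no correction.
- The pooled-error 95% interval for change to 24 months covers 83-92% under decaying correlation with constant variance. The lowest figure comes from the slowest pure decay.

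**Is the visit spacing to blame?** For the three pure-decay cases epsilon is 0.51, 0.43 and 0.38 at the planned visits, and 0.54, 0.45 and 0.39 at eight equally spaced visits over 24 months. The spacing adds little; the decay itself drives the result.

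**The case against.** The strongest reply is that the plan's wording, differences between groups, fits the group main effect best, and that test holds its level without correction. This stands. Group-by-time is not named in the documents; it is inferred from the objective in section 2. The inference is reasonable, because an average over visits cannot meet that objective.

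A reader might infer three stronger things that the documents do not support:
- *That the stated 0.05 fails.* The documents give no correlations and do not say that the test will be uncorrected. A repeated measures ANOVA may be run with an epsilon correction. The defect is incomplete specification.
- *That long-term confidence intervals will be too narrow.* None are described, and neither is a pooled-error contrast. The 7-14% figure applies only if change contrasts borrow the pooled within-patient error. For the plain between-arm difference at 24 months, an interval using the pooled cell variance covers about 95% if variance is constant, and about 89-90% if variance doubles by 24 months.
- *That unequal visit spacing causes the problem.* The epsilon comparison above shows that it is not the main cause.

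It is also fair to say that the largest figures come from structures with no measurement noise, which is unlikely for patient questionnaires. With noise, the inflation of the F test is roughly 1 to 2 points, slightly more in the worst run. Greenhouse-Geisser alone would repair that test, so preferring a mixed model for it is partly a matter of choice.

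**Conclusion.** The concern holds conditionally. Section 9 leaves the tested effect, the covariance assumption and the error term open, and the analyses that the objective needs depend on them. If correlation decays with time and no correction is made, the group-by-time test runs at about 6-7% with measurement noise and up to about 9-10% without it. If change contrasts use the pooled error, the 24-month contrast rejects about 7-14% of the time and the 1-month contrast is too conservative. With equal variances and equal correlations there is no error, and the group main effect is unaffected in every case. The sizes rest on assumed correlations. Severity is minor to moderate: the likely inflation is modest, but it touches the long-term comparisons and is easily removed.

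**What to change.** In section 9, name the effect to be tested and replace the ANOVA by a group-by-visit model with an unstructured within-patient covariance, fitted by REML with Kenward-Roger degrees of freedom. Take the between-group difference and its confidence interval at each visit from that model, and say whether baseline is one of the occasions.

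If ANOVA is kept, state that the group-by-time test will be Greenhouse-Geisser corrected and that every comparison at a single visit will use that visit's own error term.

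The cost is a few sentences and standard statistical software, which should be named because section 8 mentions only a spreadsheet. No new data are needed and the sample size does not change. The downside is fewer error degrees of freedom. With 48 complete per arm, a contrast at one visit would have 96 − 2 = 94 in place of the pooled 94 × 7 = 658, which moves the critical t value only from about 1.96 to 1.99.
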